8.11.1. Medwatch 3500A Reporting Guidelines

In addition to completing appropriate patient demographic (Section A) and suspect medication information (Section C & D), the report should include the following information within the Event Description (Section B.5) of the MedWatch 3500A form:

- Protocol number and title description
- Description of event, severity, treatment, and outcome if known
- Supportive laboratory results and diagnostics (Section B.6)
- Investigator's assessment of the relationship of the adverse event to each investigational product and suspect medication

8.11.2. Follow-up Information

Each serious adverse event must be followed up until resolution or stabilization, by submission of updated reports. Additional information may be added to a previously submitted report by any of the following methods:

- Adding to the original MedWatch 3500A report and submitting it as follow-up
- Adding supplemental summary information and submitting it as follow-up with the original MedWatch 3500A form
- Summarizing new information and faxing it with a cover letter including patient identifiers (i.e. D.O.B. initial, patient number), protocol description and number, if assigned, brief adverse event description, and notation that additional or follow-up information is being submitted (The patient identifiers are important so that the new information is added to the correct initial report)

8.12. HonorHealth Reporting to Genentech and Bayer

HonorHealth will forward quarterly listings of non-serious AEs originating from the Study to Bayer/Genentech.

HonorHealth will be responsible for collecting all protocol-defined Adverse Events (AEs)/Serious Adverse Events (SAEs), pregnancy reports (including pregnancy occurring in the partner of a male study subject), other Special Situation reports, AESIs and Product Complaints with an AE where the patient has been exposed to the Product. The completed MedWatch form should be sent to the Bayer/Genentech contact specified below. Transmission of these reports (initial and follow-up) will be either electronically via email or by fax and within the timelines specified below.

Bayer Safety Global Pharmacovigilance – USA Bayer Ref #: IRR-US-000177 [contact] [contact] Email: [contact]
 
Genentech SAE Reporting Genentech Ref# ML-42826 [contact] [contact] Email: [contact]
 
Product Complaints without AE should call via PC [contact] (M-F: 5am to 5pm PST)

Transmission of these reports (initial and follow-up) will be either electronically or by fax and within the timelines specified below:

Type of Report	Timelines
Serious Adverse Events (related and not related to the Product)	30 calendar days from awareness date
Special Situation Reports (With or without AE and pregnancy)	
Product Complaints (With or without AE)	
AESI	

Case Transmission Verification of Single Case Reports

- The parties will verify that all single case reports have been adequately received by Bayer and Genentech via HonorHealth emailing Bayer and Genentech a

Quarterly line-listing documenting single case reports sent by HonorHealth to Bayer and Genentech in the preceding time period.

- The periodic line-listing will be exchanged within seven (7) calendar days of the end of the agreed time period. Confirmation of receipt should be received within the time period mutually agreed upon.
- If discrepancies are identified, the Sponsor and Genentech will cooperate in resolving the discrepancies. The responsible individuals for each party shall handle the matter on a case-by-case basis until satisfactory resolution. The sponsor shall receive reconciliation guidance documents within the 'Activation Package'.
- Following Case Transmission Verification, single case reports which have not been received by Genentech shall be forwarded by HonorHealth to Genentech within five (5) calendar days from request by Genentech.

At the end of the study, a final cumulative Case Transmission Verification report will be sent to Bayer and Genentech

9. DRUG / TREATMENT INFORMATION

9.1. Vemurafenib

Package Insert:

https://www.accessdata.fda.gov/drugsatfda_docs/label/2020/202429s019bl.pdf

Other names for the drug:

- Zelboraf®;
- propane-1-sufonic acid {3-[5-(4-chlorophenyl)-1H-pyrrolo[2,3-b]pyridine-3-carbonyl]-2,4-difluoro-phenyl}-amide
- C₂₃H₁₈ClF₂N₃O₃S molecular weight 489.9.

Classification - type of agent: A kinase inhibitor

Mode of action: Vemurafenib is a low molecular weight, orally available, inhibitor of some mutated forms of BRAF serine-threonine kinase, including BRAF V600E. Vemurafenib also inhibits other kinases in vitro such as CRAF, ARAF, wild-type BRAF, SRMS, ACK1, MAP4K5 and FGR at similar concentrations. Some mutations in the BRAF gene including V600E result in constitutively activated BRAF proteins, which can cause cell proliferation in the absence of growth factors that would normally be required for proliferation. Vemurafenib has anti-tumor effects in cellular and animal models of melanomas with mutated BRAF V600E.

Storage and stability: Vemurafenib tablets are to be stored in their original container with lids tightly closed at room temperature 20°C-25 °C (68 °F-77 °F). Storage temperature excursions are permitted between 15°C-30 °C (59°F-86 °F).

Protocol dose: 480 mg PO (2 x 240mg tablets) BID

Preparation: No preparation required.

Route of administration for this study: Oral

Availability: Provided by Genentech free of charge.

Patient Counseling Information:

- Advise the patient to read the FDA-approved patient labeling (Medication Guide) before starting vemurafenib.
- Advise the patient to avoid consuming grapefruit and grapefruit juice while take vemurafenib during study treatment as this may raise the levels of vemurafenib and could make side effects worse.
- Advise the patient to avoid the use of St. John's Wort while taking vemurafenib during study treatment as this may lower the levels of the drug, which can make it less effective.
- Vemurafenib increases the risk of developing new primary cutaneous malignancies. Patients should be advised of the importance of contacting their healthcare provider immediately for any changes in their skin.
- Anaphylaxis and other serious hypersensitivity reactions can occur during treatment and upon re-initiation of treatment with vemurafenib. Patients should be advised to stop taking vemurafenib and to seek immediate medical attention for symptoms of anaphylaxis and hypersensitivity.
- Severe dermatological reactions can occur in patients receiving vemurafenib. Patients should be advised to stop taking vemurafenib and to contact their health-care provider for severe dermatologic reactions.
- Vemurafenib can prolong QT interval, which may result in ventricular arrhythmias. Patients should be advised of the importance of monitoring their electrolytes and the electrical activity of the heart (via and ECG) during treatment with vemurafenib.
- Liver injury leading to functional hepatic impairment, including coagulopathy or other organ dysfunction, can occur with vemurafenib. Patients should be advised of the importance of laboratory monitoring of their liver during treatment with vemurafenib and to contact their health-care provider for relevant symptoms.
- Vemurafenib can cause mild to severe photosensitivity. Patients should be advised to avoid sun exposure, wear protective clothing, use a broad-spectrum UVA/UVB sunscreen and lip balm (SPF≥30) when outdoors to help protect against sunburn.
- Ophthalmologic reactions can occur in patients treated with vemurafenib. Patients should be advised to contact their health care provider immediately for ophthalmologic symptoms.

- Due to potential risk to a fetus woman of child-bearing potential must use effective contraception during treatment with vemurafenib and for 2 weeks after their last dose.
- If a female patient confirms or suspects pregnancy during the study, they should contact their healthcare provider immediately. Any confirmed pregnancy is to be reported within 24 hours as per Section 8.6.
- If a male patient's sexual partner becomes pregnant during the study, they should contact their healthcare provider immediately. Any confirmed pregnancy is to be reported within 24 hours as per Section 8.6.
- Female patients should be advised not to breastfeed during treatment with vemurafenib and for 2 weeks following the final dose.
- Radiation sensitization and recall can occur in patients treated with radiation prior to, during, or after treatment with vemurafenib. Patients should be advised to inform their health care provider if they have had or are planning to receive radiation therapy. Radiotherapy may be allowed while the patient is enrolled in this study if given to help palliate a specific symptom (e.g. bone pain, brain metastases, etc.
- Renal failure can occur in patients treated with vemurafenib. Patients should be advised of the importance of monitoring serum creatinine prior to and during treatment with vemurafenib.
- Advise patients to contact their health care provider for symptoms of Dupuytren's contracture or plantar fascial fibromatosis

9.2. Sorafenib

Package Insert:

https://www.accessdata.fda.gov/drugsatfda_docs/label/2018/021923s020lbl.pdf

Other names for the drug(s):

- Nexavar
- Sorafenib tosylate
- 4-(40{3-[4-Chloro-3-(trifluoromethyl)phenyl]ureido}ogebixt)N2-methylpyridine-2-carboxamide 4-methylbenzenesulfonate
- C₂₁H₁₆ClF₃N₄O₃ x C₇H₈O₃S

Classification - type of agent: Kinase inhibitor

Mode of action: Sorafenib is a kinase inhibitor that decreases tumor cell proliferation in vitro. Sorafenib was shown to inhibit multiple intracellular (c-CRAF, ARAF and mutant BRAF) and cell surface kinases (KIT, FLT-3, RET, RET/PTC, VEGFR-1, VEGFR-2, VEGFR-3, and PDGFR-β). Several of these kinases are thought to be involved in tumor cell signaling, angiogenesis, and apoptosis. Sorafenib inhibited tumor growth of HCC, RCC and DTC human tumor xenografts in immunocompromised mice. Reductions in

tumor angiogenesis were seen in models of HCC and RCC upon sorafenib treatment and increases in tumor apoptosis were observed in models of HCC, RCC and DTC.

Storage and stability: The tablets should be stored in a dry place at 25 °C (77 °F). Storage temperature excursions are permitted between 15°C-30 °C (59 °F-86 °F).

Protocol dose: 200mg (one tablet) PO am and 200mg (one tablet) PO pm

Preparation: No preparation is required

Route of administration for this study: Oral

Availability: Provided by Bayer free of charge.

Patient Counseling Information:

- Patients should be advised to read the FDA approved patient labelling guide prior to starting treatment with sorafenib.
- Discuss with patients that cardiac ischemia and/or infarction and congestive heart failure, have been reported during sorafenib treatment and that they should immediately report any episodes of chest pain or other symptoms of cardiac ischemia or congestive heart failure.
- Inform patients with a history of prolonged QT interval that sorafenib can worsen the condition.
- Inform patients that sorafenib can increase the risk of bleeding and that they should promptly report any episodes of bleeding.
- Inform patients that bleeding, or INR elevations have been reported in some patients taking warfarin while on sorafenib and that their INR should be monitored regularly.
- Inform patients that hypertension can develop during sorafenib treatment, especially during the first six weeks of therapy and that blood pressure should be monitored regularly during treatment.
- Patients should be advised of the possible occurrence of hand-foot skin reaction and rash during sorafenib treatments and the measures they should take.
- Patients should be advised that cases of gastrointestinal perforation have been reported in patients taking sorafenib.
- Patients should be informed that temporary interruption of sorafenib is recommended in patients undergoing major surgical procedures due to potential wound healing complications.
- Sorafenib can cause hepatitis which may result in hepatic failure and death. Patients should be advised that liver function tests should be monitored regularly during treatment and that they should report symptoms of hepatitis.

- Due to potential risk to a fetus woman of child-bearing potential must use effective contraception during treatment and for 6 months after the last dose of sorafenib. Male patients with female partners of reproductive potential or who are pregnant must use effective contraception during treatment with sorafenib and for 3 months after receiving their last dose.
- If a female patient confirms or suspects pregnancy during the study, they should contact their healthcare provider immediately.
- Patients on sorafenib should not breastfeed while taking the medication and for 2 weeks after receiving their last dose.
- If a patient misses a dose of sorafenib, the next dose should be taken at the regularly scheduled time; they should not double the dose. Patients should be instructed to contact their healthcare provider immediately if they take too much sorafenib.

9.3. Return and Retention of Study Drug

Institutional pharmacy standard operating procedures will be followed for retention, storage, and destruction of study drug.

9.4. Drug Accountability

Patients will be instructed to complete a study drug diary and return along with the study medication bottles on Day 1 visit of each cycle for drug accountability. Drug accountability will be completed by delegated study personnel at minimum of once per cycle by reviewing both the patient completed drug diary and the returned study medication. Study personnel will document any missed doses in the source documents and review this with both the patient and the treating investigator. Study personnel will provide additional reinstruction to the patient and implement additional drug accountability throughout a cycle as needed.

10. CORRELATIVES / SPECIAL STUDIES

10.1. Trial Specimens

Blood specimens will be collected for plasma DNA to determine target engagement before, during and after treatment. This will be measured at baseline and just before each cycle of treatment. The site will collect blood samples (3 X 10 mL) at screening, Day 1 of each treatment cycle, and at the off treatment study visit.

Please see Laboratory Manual for details on blood collection and processing guidelines.

10.2. Assay Methodology

Blood samples will be collected and processed for plasma at baseline and just before each treatment cycle. Plasma will be used to analyze circulating tumor DNA (ctDNA) to give qualitative (mutations) and to some extent quantitative (amount of ctDNA) information regarding BRAF and KRAS.

Blood samples will be collected and processed for serum at baseline and just before each treatment cycle. Serum will be analyzed using the Bio-plex suspension array using specific antibodies and flow cytometry as per the methods developed by Takano et al. 2010 to measure phospho ERK to determine if the treatment has hit the intended target.

Tissue samples

For those patients that consent to the optional tissue collection for RPPA analysis, tissue will be collected from a newly obtained core or excisional biopsy of a tumor lesion if performed recently (within 30 days prior to study treatment on Day 1) and during their participation in the study should they be scheduled for a biopsy as part of their routine care during their participation in the study through the follow-up period.

Tissue samples will be analyzed using Reverse Phase Protein Array (RPPA).

10.3. Specimen Banking

Any blood samples remaining after the trial specified analyses is completed will be transferred to and stored at HonorHealth if the patient consented for use of their remaining samples for future research purposes at HonorHealth's discretion. This includes the original specimen collected from the patient as well as derivatives created from the original specimen (DNA, RNA).

11. STATISTICAL CONSIDERATIONS

11.1. Study Design / Study Endpoints

This is a phase II open-label, single arm trial, with the identity of the treatment known to the patients, Investigators, and Sponsor.

11.2. Sample Size and Accrual

Between 7 and 12 evaluable patients total will be entered into this study. To obtain that number of evaluable patients we estimate up to 24 patients will possibly be enrolled. An evaluable patient is defined as one that receives at least one dose of both agents (vemurafenib + sorafenib) and has a scan after at least 2 cycles of treatment. We are hoping for a disease control rate of $\geq 40\%$. Simon's two-stage design (Simon, 1989) will be used. The null hypothesis that the true response rate is 5% will be tested against a one-sided alternative. In the first stage, $n=7$ patients will be accrued. If there are zero responses in these 7 patients, the study will be stopped. Otherwise, 5 additional patients will be accrued for a total of 12. The null hypothesis will be rejected if 3 or more responses are observed in 12 patients. This design yields a type I error rate of 0.0188 and power of 0.9077 when the true response rate is 40%. (Jung et al, 2004).

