5.9. Subject Replacement

Patients who receive any number of doses of both agents (Vemurafenib + Sorafenib) and has a scan after at least 2 cycles of treatment will not be replaced. Therefore, any

patient that does not meet this criteria will be replaced in order to achieve 7 evaluable patients.

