6.3.3. Tumor Assessments Every 2 Cycles (Every 8 Weeks)

- Tumor measurements per RECIST 1.1 (before C3, C5, C7 etc.). Tumor measurements may be obtained at the discretion of the principal investigator if clinically indicated.
- CA19-9 (or CA 125, or CEA if not expressers of CA 19-9) before C3, C5, C7 etc.)

In order to more precisely determine time to progression, the investigator is encouraged to obtain radiological assessments earlier if there is a strong clinical suspicion of disease progression, in order to either confirm or refute the clinical impression.

Reassessment of the extent of tumor should be made by the same imaging methods used to establish baseline tumor measurements.

6.4. Off Treatment Visit – to be Completed 14-28 (+/-2) Days From the Last Dose of Study Treatment

- Directed physical exam, if deemed necessary
- Weight (kg)
- Vital signs (blood pressure, pulse, respiratory rate, and temperature)

- ECOG Performance status
- Hematology: CBC with differential and platelet count
- Serum chemistries: glucose, creatinine, BUN, total bilirubin, AST, ALT, alkaline phosphatase albumin, LDH, total protein, and electrolytes (sodium, potassium, phosphorus, chloride, CO₂, magnesium, calcium). In patients with known Gilbert's syndrome, it is recommended to perform a direct bilirubin and indirect bilirubin. Calculate creatinine clearance (Cockcroft-Gault equation).
- Coagulation: PT, INR– only required for patients on warfarin
- CA19-9 (or CA 125, or CEA if not expressers of CA 19-9)
- Serum pregnancy if applicable
- Blood for correlative analysis- 3 X 10 mL
- AEs using the NCI CTCAE 5.0
- Concomitant medication notation
- Complete Drug Accountability (Per Section 9.4): Collect all previously distributed study medications and review the completed Patient Study Drug Diary with the patient and address any discrepancies with the patient.
- Confirm contact information for patient and a designated family member, and primary care physician and remind patient of follow-up telephone contact that will be conducted 30 days after the last dose of study treatment and then every 3 months for survival status.

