7. MEASUREMENT OF EFFECT

7.1. Disease Control Rate

Disease control rate (defined as CR + PR + Stable x16 weeks) will be evaluated using the RECIST criteria (version 1.1, 2009) proposed by the RECIST committee.

These response criteria are widely recognized and accepted as the standard criteria for determining response in patients with solid tumors.

https://ctep.cancer.gov/protocolDevelopment/docs/recist_guideline.pdf

All patients who have measurable disease according to the RECIST criteria and who have their disease re-evaluated will be evaluable for response.

For the purposes of this study, patients should be reevaluated for response approximately every 2 cycles.

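### The primary disease control rate counts only patients scanned after at least 2 cycles and replaces the rest, so the stated 0.0188 type I error does not carry over to all treated patients

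*Combined protocol and SAP*

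**What the plan says.** The primary endpoint is disease control (CR, PR or stable disease) at 16 weeks. Section 11.2 makes a patient evaluable if that patient "receives at least one dose of both agents (vemurafenib + sorafenib) and has a scan after at least 2 cycles of treatment". The Synopsis and Sections 11.3.2 and 11.3.4 use the same test in nearly the same words, and Section 11.3.4 confines the efficacy analysis to patients who meet it.

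Under Section 5.9, any "patient that does not meet this criteria will be replaced in order to achieve 7 evaluable patients". That sentence names only the first 7, but the total of 12 evaluable patients in the Synopsis and Section 11.2 implies replacement in stage 2 as well.

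The stage 1 rule in Section 11.2 is: "If there are zero responses in these 7 patients, the study will be stopped". If the trial goes on, stage 2 brings the number from 7 to 12. The final rule is: "The null hypothesis will be rejected if 3 or more responses are observed in 12 patients". The section tests a null rate of 5% against a hoped-for 40% and states a type I error of 0.0188 and power of 0.9077. On enrolment it says: "To obtain that number of evaluable patients we estimate up to 24 patients will possibly be enrolled".

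Two other sections bear on who is counted. Scans fall before cycles 3, 5 and 7, but Section 6.3.3 adds that "the investigator is encouraged to obtain radiological assessments earlier if there is a strong clinical suspicion of disease progression". Section 7.1 has a wider rule: "All patients who have measurable disease according to the RECIST criteria and who have their disease re-evaluated will be evaluable for response".

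**The concern.** Entry to the primary denominator depends on something that happens after treatment starts: lasting about 8 weeks and then being scanned. A patient who dies, declines clinically or stops for toxicity before that scan is replaced. So is a patient whose progression is documented on an early scan of the kind Section 6.3.3 encourages and who then stops. Section 7.1 would count that last patient, so the plan holds two different denominators for one endpoint.

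No section counts these early exits as failures, and no disease control analysis of all treated patients is planned. Section 11.3.2 promises only a count of those who do not qualify.

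The reported rate, the stage 1 stop and the 3-of-12 rule all rest on this selected set. The objective in Section 3.1 concerns patients with advanced KRAS-mutated refractory pancreatic cancer, not those who reach a scan after 2 cycles. In a single-arm trial no control group would expose the difference, and with a threshold of 3 successes a few uncounted failures can change how the result reads.

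**Working it through.** **Inputs (Section 11.2).** Stage 1: 7 patients, stop at 0 successes. Stage 2: 5 more. Success: 3 or more of 12. Null 5%, target 40%. Enrolment ceiling 24.

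**Formula.** With success probability p per counted patient,

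P(reject) = Σ over x = 1 to 7 of P(X1 = x) × P(X2 ≥ 3 − x), where X1 ~ Bin(7, p) and X2 ~ Bin(5, p).

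**Reproducing the plan's figure, p = 0.05.**
- x = 1: 0.2573 × 0.0226 = 0.0058
- x = 2: 0.0406 × 0.2262 = 0.0092
- x ≥ 3: 0.0038
- Sum: 0.0188, as stated. At p = 0.40 the same formula gives 0.9077, also as stated.

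**Moving from evaluable to treated patients.** Let q be the share of treated patients who become evaluable, p_T the disease control rate among all treated patients, and c the rate among excluded patients. Then p_T = q × p_E + (1 − q) × c, so the rate among evaluable patients is p_E = (p_T − (1 − q) × c) / q. If excluded patients have no control at 16 weeks (c = 0), p_E = p_T / q. The documents give no value for q, so it is varied here.

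**Results for p_T = 0.05 and c = 0.**

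| q | p_E = 0.05/q | P(reject) | P(stop at stage 1) = (1 − p_E)^7 |
|---|---|---|---|
| 1.0 | 0.0500 | 0.0188 | 0.698 |
| 0.9 | 0.0556 | 0.025 | 0.670 |
| 0.75 | 0.0667 | 0.040 | 0.617 |
| 0.6 | 0.0833 | 0.069 | 0.544 |
| 0.5 | 0.1000 | 0.107 | 0.478 |

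Check at q = 0.5: 0.3720 × 0.0815 + 0.1240 × 0.4095 + 0.0257 = 0.0303 + 0.0508 + 0.0257 = 0.107. P(reject) exceeds 0.05 once q falls below about 0.68.

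The row q = 0.5 is 12/24. It treats the enrolment ceiling as if it were the number treated.

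**Effect on the estimate.** At q = 0.5 and c = 0, a 20% all-treated rate shows as 0.20/0.5 = 40%. A result of 3/12 = 25% among evaluable patients would be 3/24 = 12.5% of 24.

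**Power if the 40% was meant for evaluable patients.** With 12 treated patients as denominator, the success probability is 0.40 × q. At q = 0.75 this is 0.30 and power is 0.73; at q = 0.5 it is 0.20 and power is 0.43.

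**The case against.** **The 0.0188 is not a miscalculation.** A reader might infer that it is. It reproduces exactly, and the plan defines evaluable patients the same way in the Synopsis and Section 11. No section says that 5% or 40% is a rate among all treated patients. This stands: the valid point is that the figure does not transfer to the treated population.

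**The error need not run only upward.** A patient who stops both drugs for toxicity in the first 2 cycles could still be stable at week 16. No scan is scheduled at the off-treatment or follow-up visits, so that status may never be known. This stands: p_T / q assumes that every excluded patient is a failure. If excluded patients had the same rate as the rest (c = p_T), p_E would equal p_T and there would be no inflation.

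**A share of 0.5 is not the plan's forecast.** The 24 is a ceiling on patients enrolled, and Section 11.3.2 foresees some who never start treatment. This stands, so 0.107 is an upper bound.

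**Not all early progressors are lost.** Progression found on the scheduled week-8 scan is kept as a failure. Nor does early progression escape oversight: progression of RAS-mutant malignancies is an event of special interest (Section 8.7), the monitoring committee reviews such events (Section 12.10.1), and safety analyses cover everyone dosed (Section 11.3.5). The gap is in the efficacy denominator.

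**The Synopsis gives a competing design.** Its Statistical Methods state 5+7 patients, success defined as PR or CR, and a 0% null. Under a 0% null the rejection probability is zero whatever q is, so the figures above hold only if Section 11.2 governs. They do not settle which design does.

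**Conclusion.** The concern holds in this form. The primary rate and both decision rules rest on a set chosen by a post-treatment event, early exits are replaced rather than counted as failures, and Section 7.1 contradicts the definition used elsewhere.

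For a 5% all-treated rate, the chance of declaring success lies between the stated 0.0188 (everyone evaluable) and 0.107 (half evaluable), with 0.025, 0.040 and 0.069 at shares of 0.9, 0.75 and 0.6. This rests on three assumptions: the 7+5 design of Section 11.2 applies, excluded patients lack 16-week control, and the share lies between 0.5 and 1. The documents fix none of the last two. The denominator rule is clear from the text; the size of its effect is not.

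**What to change.** - **Denominator.** For the primary rate, the stage 1 rule and the final rule, use every patient who received at least one dose of both drugs. Count a patient without documented control at 16 weeks as not controlled, whether because of progression, death, withdrawal or no scan.
- **Replacement.** Limit Section 5.9 to patients who never received both drugs.
- **Consistency.** Align the Synopsis with Sections 5.9, 7.1, 11.2, 11.3.2, 11.3.4 and 11.4. Keep the current evaluable set as a labelled sensitivity analysis.
- **Reference rates.** State whether 5% and 40% refer to all treated patients. If they do, 0.0188 and 0.9077 hold for the 12 treated patients. If 40% was meant for evaluable patients, restate the power for 12 treated patients (0.73 at a share of 0.75, 0.43 at 0.5) rather than enrol more.
- **Design.** Reconcile the 7+5 design in Section 11.2 with the 5+7 design in the Synopsis, and say which patients each covers.

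**Cost.** This is a change of wording and analysis that needs no added patients. The reported rate will be less favourable, and the power may be too. Counting an unscanned but stable patient as a failure is conservative, which the sensitivity analysis helps to show. Section 1.4 shows that patients have already been treated, so the change must be documented as an amendment and applied to all treated patients, not only to later ones.

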11.3.4. Statistical Analysis

The primary efficacy analysis will focus on the disease control rate (CR + PR + SD at 16 weeks). Secondary endpoints include progression-free survival (PFS) and overall survival (OS). The efficacy analysis will only be conducted on patients who have received any number of doses of both agents (vemurafenib + sorafenib) and have a scan after at least 2 cycles of treatment.

Objective responses will be evaluated using the Response Evaluation Criteria In Solid Tumors 1.1 (RECIST 1.1). Changes (i.e. improvements) in tumor measurements from baseline values will be assigned a status of CR or PR or SD. Objective response measurements will comprise the sum of CR plus PR. The overall response rate, as well as the rates for the individual categories of response (i.e. CR, PR, SD, and PD), will be estimated by the percentage of patients achieving these criteria with exact 95% binomial confidence intervals.

Progression-free survival is defined as the interval from the date of study treatment initiation (C1/D1) to the earliest date of documented evidence of recurrent or progressive disease, or the date of death due to any cause, whichever occurs first. Overall survival will be measured from the date of study treatment initiation (C1/D1) to the date of death

due to any cause, or the date of last contact (censored observations). For the estimation of progression-free and overall survival a Kaplan-Meier analysis will be performed.

Longitudinal measurements of circulating tumor DNA (ctDNA) and phospho ERK will be visualized using plots for each evaluable patient. These measurements will be transformed using a logarithmic transformation, if necessary, to remove skewness. Significant changes across time will be assessed using linear mixed effects models, to account for the correlation among the measurements within an individual. If the observed change is non-linear, nonlinear mixed effects models will be used.

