11.4. Stopping Rules

The study can be stopped early based on the following criteria:

- Per PI or sponsor discretion
- If none of the first 7 evaluable patients have disease control (CR+ PR +SD at 16 weeks)

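### Section 11.2 counts undefined *responses* although the primary endpoint is 16-week disease control, and nothing in the plan ties the 3-of-12 success cutoff to disease control

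*Combined protocol and SAP*

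**What the plan says.** **Endpoint.** Section 11.3.4 states: "The primary efficacy analysis will focus on the disease control rate (CR + PR + SD at 16 weeks". The synopsis and Sections 3.1, 3.4.1 and 7.1 also name disease control as the primary measure.

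**Design.** Section 11.2 introduces the sample size with "We are hoping for a disease control rate of" at least 40%. It then changes terms without defining the new one:
- Null: "The null hypothesis that the true response rate is 5% will be tested against a one-sided alternative".
- Stage 1: "If there are zero responses in these 7 patients, the study will be stopped".
- Final cutoff: "The null hypothesis will be rejected if 3 or more responses are observed in 12 patients".
- Operating characteristics: type I error 0.0188, and power 0.9077 at a response rate of 40%.

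**Stage 1 elsewhere.** Section 11.4 lists as a reason to stop: "If none of the first 7 evaluable patients have disease control", meaning CR, PR or SD at 16 weeks. The synopsis entry on number of patients says the same.

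**Final cutoff elsewhere.** The synopsis Statistical Methods has a 3-of-12 rule that says what a response is: PR or CR. It sits in another design, introduced after a note to file, with a 0% null and stages of 5 and then 7 patients.

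**Use of the word response.** Section 11.3.4 says "Objective response measurements will comprise the sum of CR plus PR". In the same paragraph it lists CR, PR, SD and PD as categories of response. Exact 95% intervals are specified there for the overall response rate and for each of those four categories. The disease control rate is not on that list.

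**The concern.** The rule that decides whether the trial succeeds should count the primary endpoint. Section 11.2 does not say that it does. A reader who looks elsewhere for the meaning of *responses* in the final cutoff finds one explicit definition attached to a 3-of-12 rule, and it excludes stable disease.

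Two things are at stake. The stated power holds only if the counted event occurs in 40% of patients, and the only 40% target in the plan is for disease control. A regimen whose benefit is mainly stable disease could meet that target and still fail a CR+PR count. In addition, the trial is open-label and single-arm. If the counted event is settled only after the outcomes are known, the test is no longer prespecified.

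**Working it through.** **Inputs.** Section 11.2 gives 7 patients at stage 1, a stop at 0, then 5 more for a total of 12, and rejection at 3 or more. The null rate is 5% and the target 40%. The documents give no expected CR+PR rate, so 10%, 15% and 20% are assumptions.

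**Formula.** The null is rejected if at least 3 of 12 succeed, except where stage 1 has none and all the successes fall in stage 2:

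P(reject) = P(Bin(12, p) ≥ 3) − (1 − p)^7 × P(Bin(5, p) ≥ 3)

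P(stop at stage 1) = (1 − p)^7

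**Reproducing the plan's figures.**
- p = 0.05: 0.01957 − 0.69834 × 0.00116 = 0.0188, as stated.
- p = 0.40: 0.91656 − 0.02799 × 0.31744 = 0.9077, as stated.

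The arithmetic does not depend on the name of the event. If the event is disease control, both figures stand.

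**If CR plus PR is counted at both stages.**

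| Assumed CR+PR rate | P(Bin(12) ≥ 3) | (1 − p)^7 | P(Bin(5) ≥ 3) | P(reject) |
|---|---|---|---|---|
| 10% | 0.11087 | 0.47830 | 0.00856 | 0.107 |
| 15% | 0.26418 | 0.32058 | 0.02661 | 0.256 |
| 20% | 0.44165 | 0.20972 | 0.05792 | 0.430 |

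The third column is the stage 1 stopping chance on this reading, against 0.028 at 40%.

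**If stage 1 counts disease control, as Section 11.4 and the synopsis say, and only the final cutoff counts CR plus PR.** With true disease control at 40%, the stage 1 stop has probability 0.6^7 = 0.02799, and P(reject) = P(Bin(12, q) ≥ 3) − 0.02799 × P(Bin(5, q) ≥ 3), where q is the CR+PR rate:
- q = 10%: 0.11087 − 0.02799 × 0.00856 = 0.111
- q = 15%: 0.26418 − 0.02799 × 0.02661 = 0.263
- q = 20%: 0.44165 − 0.02799 × 0.05792 = 0.440

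So settling stage 1 recovers almost nothing. The loss comes from the final cutoff.

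**One data set, two conclusions.** Take 12 evaluable patients with 1 PR and 4 SD at 16 weeks, the PR being among the first 7 so that the trial continues on either count. Disease control is 5/12 = 42%, above the target, and 5 ≥ 3 rejects the null. The CR+PR count is 1, and 1 < 3 does not reject.

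**If the synopsis 5+7 staging governs.** The same method with stages of 5 and 7 gives P(reject) = 0 at the 0% null stated there, 0.0167 at 5% and 0.871 at 40%. The figures in Section 11.2 do not carry over to that design.

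**The case against.** The strongest reply is that Section 11.2 plainly means disease control. Its only 40% target is a disease control rate, its power is computed at 40%, and the primary analysis is of disease control. *Response* is then loose wording for a success on the primary endpoint. This stands as the likely intent, and on it the stated error rates are right.

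It also disposes of stronger readings that a reader might infer:
- *That Section 11.3.4 equates responses with CR plus PR, so the primary test as written ignores stable disease.* Section 11.3.4 defines objective response, a term that Section 11.2 does not use, and it counts SD among the categories of response.
- *That the stage 1 stop is open to a CR+PR count.* Section 11.4 and the synopsis entry on number of patients both give the 7-patient stop as disease control. The higher stage 1 stopping chances in the table therefore describe a rule that two places contradict.
- *That the stated power is wrong.* It reproduces exactly. The low figures depend on the CR+PR reading and on assumed rates.

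What the reply cannot supply is a statement of the final cutoff in disease control. There is none, and the synopsis has a 3-of-12 rule that expressly counts PR or CR. Likely intent is not a prespecified rule when the same document also states the other one.

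**Conclusion.** The concern holds as an inconsistency in the counted event of the primary test, confined mainly to the final cutoff. It is not an error in the calculation. With disease control counted and the 7+5 design kept, type I error is 0.0188 and power 0.9077. With CR plus PR counted at both stages, the chance of success is 0.107 to 0.430 for assumed CR+PR rates of 10% to 20%. It is 0.111 to 0.440 if only the final cutoff is counted that way and true disease control is 40%. Which reading applies can reverse the trial's conclusion, so the wording should be settled before the primary analysis.

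The absence of an exact interval for the disease control rate is a smaller, separate gap: the primary estimate has no stated measure of precision.

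**What to change.** 1. In Section 11.2, replace the response rate with the 16-week disease control rate, and responses with patients who have disease control (CR+PR+SD) at 16 weeks. Do this in the null, the stage 1 stop, the final cutoff and the power statement. That agrees with the primary endpoint and Section 11.4.
2. Reconcile the synopsis Statistical Methods with the synopsis entry on number of patients and with Sections 11.2 and 11.4, so that one endpoint, one null rate and one set of stage sizes govern the primary test. Rewording Section 11.2 alone would leave the conflict in place.
3. In Section 11.3.4, add the disease control rate, as the primary estimate, to the rates that receive an exact 95% interval.

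If disease control with the 7+5 design is kept, the cost is wording only: no patients, no procedures and no change in the stated error rates. If the sponsor states that the 5+7 design with PR or CR governs, the primary endpoint statement and the operating characteristics must be restated to match.
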